Medication dispensing and delivery: Medications will be dispensed and delivered in such a manner that (a) all study personnel, nurses and technicians in the Clinical Research Unit, (b) the study staff and investigators directly involved in this research, and (c) the participants will be blinded to the nature of the study medication. The nursing personnel of the Clinical Research Unit will dispense the medication guide instructions and will provide the subject education on the proper administration of the study medication prior to start of dosing. A "Direction for Use" pamphlet will be given to subjects, who will be instructed how to use liraglutide and placebo.

Quantitative Traits

On different days, participants will attend the Mayo Clinic Clinical Research Trials Unit (CRTU) at scheduled time after an 8-hour fasting period, and the following validated quantitative traits will be measured:

1. **GE of solids** by scintigraphy: The primary endpoint is gastric half-emptying time (GE $T_{1/2}$), and the secondary endpoints are proportions emptied at 2 and 4 hours (Vazquez-Roque et al. 2006). The normal range for GE $T_{1/2}$ is based on 10th and 90th percentiles in healthy volunteers, based on gender (see Table 5, Camilleri et al. 2012). In general, GE of liquids is non-contributory in the context of postprandial symptoms (Sachdeva et al. 2011); in order to reduce radiation burden (needing two isotopes to assess both liquid and solid emptying), we will study exclusively GE of solids.
2. **Fasting and postprandial Gastric Volume (GV)** by single photon emission computed tomography (SPECT), developed and validated (including performance characteristics) in our lab (Bouras et al. 2002; Delgado-Aros et al. 2005; Breen et al. 2011).
3. **Satiation by Ensure® nutrient drink test** (1kcal/mL, 11% fat, 73% carbohydrate, and 16% protein) ingested at a constant rate of 30ml/min to measure volume to fullness (VTF) and maximal tolerated volume, MTV (Chial et al. 2002). Briefly, participants record their sensations every 5 minutes using a numerical scale from 0 to 5, with level 0 being no symptoms, level 3 corresponding to fullness sensation after a typical meal (VTF) and level 5 corresponding to the MTV (maximum or unbearable fullness/satiation). Nutrient intake is stopped when subjects reach the score of 5. Postprandial symptoms of fullness, nausea, bloating, and pain are measured 30 minutes after the meal using 100 mm horizontal visual analog scales, with the words "none" and "worst ever" anchored at each end.
4. **Satiety (for assessment of kcal intake as a measure of appetite)** by ad-libitum buffet meal to measure total caloric intake and macronutrient distribution in the chosen food (Vazquez-Roque et al. 2006). Five hours after ingesting 300 mL liquid nutrient (Ensure®) as part of the SPECT gastric volume study, participants will be invited to eat, during a 30-minute period, a standard *ad libitum* meal that includes:
 - a. standardized lasagna meal (Stouffers, Nestle USA, Inc, Solon, OH; nutritional analysis of each 326-g box: 420 kcal, 17 g protein [16% of energy], 38 g carbohydrate [37% of energy], and 22 g fat [47% of energy]; vanilla pudding (Hunts, Kraft Foods North America, Tarrytown, NY; nutritional analysis of each 99-g carton: 130 kcal, 1 g protein [3% of energy], 21 g carbohydrate [65% of energy], and 4.5 g fat [32% of energy]); and
 - b. skim milk (nutritional analysis of each 236-mL carton: 90 kcal, 8 g protein [36% of energy], 13 g carbohydrate [64% of energy], and 0 g fat).The total amount (grams and kilocalories) of food consumed and the kilocalories of each macronutrient at the ad libitum meal were analyzed by using validated software (ProNutra 3.0; Viocare Tech. Inc., Princeton, NJ).
Overweight or obese participants will be subdivided into "excessive eaters" [the top tertile (1176 kcal) as defined in a prior study of 264 participants] and the bottom 2 tertiles, defining non-excessive intake.
5. **Ratings of appetite** will be measured every 30 minutes between the time of ingestion of standard liquid breakfast and the start of the ad libitum meal, ratings for appetite (satiety, fullness, hunger and prospective food consumption), thirst, well-being and nausea will be recorded using visual analog scales, as described

by Flint et al. (2000). VAS, 100mm in length with words anchored at each end expressing the most positive and the most negative rating, will be used to assess hunger, satiety, fullness, prospective food consumption, desire to eat something fatty, salty, sweet or savory, and the palatability (5 questions) of the test meal. Overall appetite score will be calculated as average of the 4 individual scores (satiety + fullness + (100-prospective food consumption) + (100-hunger))/4

6. **Plasma gastrointestinal hormones (GLP-1 and PYY)** by radioimmunoassay, measured fasting, and 15, 45, and 90 minutes postprandially, with the primary endpoint being the peak postprandial level. Ghrelin and CCK levels will not be measured in proposal, since they were non-informative in our prior study.

GLP-1 will be measured as the biologically active GLP-1 (active and total) using a 2-site non-competitive immunoassay based on enzyme-labeled quantification of GLP-1 detected by a fluorogenic substrate.

PYY will be measured by radioimmunoassay (Linco Research, Inc., St. Charles, MO). PYY exists in at least 2 molecular forms, 1-36 and 3-36, both of which are physiologically active and are detected by the assay.

7. **Self-administered questionnaires** assessing affect, exercise performance, attitudes, satisfaction with body image, and eating behavior (Bush et al. 1998; Clark & King 2000; Clark et al. 2008; Lloyd-Richardson et al. 2000; Yanovski 1993; Zigmond & Snaith 1983); details of each questionnaire are provided above.

8. **Storage of biological samples:**

a. **Blood Samples** (fasting and postprandial) will be stored in a -70°C freezer in our lab for future assays.

b. **Genomic DNA** will be isolated from peripheral blood leukocytes as in previous studies (Qiagen Kit) *for possible future studies*.

9. **DEXA body composition:** Total body fat, leg fat, fat percentage, and fat free mass will be measured by DEXA scanning (QDR-2000) (Jensen et al. 1995).

10. **Liver Stiffness and fat content:** We will measure the stiffness and fat content of liver non-invasively using different ultrasound equipment at **baseline, 8 weeks and 16 weeks** in participants who provide informed consent. The GE Logiq E9 and/or the Verasonics scanner will be used to for ultrasound measurements. It is beneficial to test the measurements on different ultrasound scanners to evaluate performance. We will analyze results as we study the patients. Based on the results, we may pick one scanner (either GE or Verasonics scanner) to continue the study. Regardless whether one or two scanners are used, we will keep the ultrasound study time within 30 minutes as stated in the consent form.

General Approach for Statistical Analyses

The analyses will be based on a **2-treatment stratified design** to compare the effects of liraglutide and placebo on *post-treatment gastric functions, satiation, satiety, incretins, body composition and weight loss*; *in addition, the effects of liraglutide will be compared between* patients with (vs. without) the trait of interest (i.e., the strata being accelerated vs. normal GE of solids using the 10th percentile for GE of solids in health). The analyses will use a 2-way analysis of covariance (ANCOVA) model with treatment, the quantitative trait, and a treatment by quantitative trait interaction term.

The sample size is based on the feasibility to perform a 16-week therapeutic trial over 4 years, during which approximately 40 participants completed/ year. Year 5 of the proposed application will be necessary for completion of all trait analyses, and writing manuscripts.

Interim Analysis: As part of an on-going method to compare the effects of medication tested (liraglutide) and placebo, an interim analysis will be conducted when >66% of aim 1 has been reached.

Rationale for Interim Analysis:

a. To assess power of the study based on the actual coefficient of variation as measured in the actual study with >66% completed; this is because the coefficient of variation could be different from the COV used in the a priori power calculation used in development of the protocol.

b. As part of the analysis, the statisticians will also provide a comparison of the results on the primary and secondary endpoints; this assessment will be communicated to the investigators as average data (e.g. median and IQR) for the treatment GROUPS rather than individual patient data. These group data could be used for preparation of preliminary reports in the form of abstract for national meetings specifically digestive disease week to be held in May 2021 for which the deadline for abstract submission is December 1, 2020.

c. As a result of the power analysis, it is possible that the sample size may be either reduced or increased or the study could be stopped because of “futility” if there is no evidence of a trend to suggest efficacy of treatment

Literature Cited

Acosta A, Camilleri M, Burton D, O'Neill J, Eckert D, Carlson P, Zinsmeister AR. Exenatide in obesity with accelerated gastric emptying: a randomized, pharmacodynamics study. *Physiol Rep* 2015a Nov;3(11). pii: e12610. doi: 10.14814/phy2.12610

Acosta A, Camilleri M, Shin A, Vazquez-Roque M, Iturrino J, Burton D, O'Neill J, Eckert D, Zinsmeister AR. Quantitative gastrointestinal and psychological traits associated with obesity and response to weight-loss therapy. *Gastroenterology* 2015b;148:537-546, e4

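### The interim at more than 66% gives between-arm results to investigators before data lock and lets N change or the study stop without a written rule, so type I error control is not assured

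*Combined protocol and SAP*

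**What the plan says.** Under General Approach for Statistical Analyses, "an interim analysis will be conducted when >66% of aim 1 has been reached". Three purposes follow in Rationale for Interim Analysis.

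- (a) Power is to be reassessed, because "the coefficient of variation could be different from the COV used in the a priori power calculation used in development of the protocol".
- (b) Also, "the statisticians will also provide a comparison of the results on the primary and secondary endpoints", and "this assessment will be communicated to the investigators as average data" for the treatment groups, not for individual patients. These data may go into an abstract for which "the deadline for abstract submission is December 1, 2020". The document is dated October 29, 2020, 33 days earlier.
- (c) Once power has been reassessed, "it is possible that the sample size may be either reduced or increased or the study could be stopped because of" what the plan labels futility. The only criterion offered for that stop is qualitative: "if there is no evidence of a trend to suggest efficacy of treatment".

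The same section says of N: "The sample size is based on the feasibility to perform a 16-week therapeutic trial over 4 years". No planning COV, target difference, power or significance level appears anywhere. Overall Design, Randomization and Allocation keeps allocations concealed and the studies blinded up to transmission of the data for lock. No interim lock or exception for group results is described.

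**The concern.** Two things are at stake.

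The first is error control. Item (c) allows three actions after the arms have been compared, and nothing ties any of them to a rule. The same words cover harmless uses (N from variability only, a futility stop only) and uses that raise type I error (cutting N once the observed difference is significant, extending when it is not). A reader of the final result could not tell which had been used.

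The second is conduct. Investigators, and possibly the public, would know the group effects while participants are still being treated, counselled and measured. That knowledge cannot be withdrawn later.

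**Working it through.** The plan states no error rate, boundary or power, so there is no figure of its own to reproduce.

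**Inputs.** N = 112 (Selection of Overweight and Obese Participants). If the trigger means patients, 0.66 × 112 = 73.9, so at least 74. Assumptions not in the documents: two-sided 0.05 (critical value 1.96), 1:1 allocation (56 per arm), a look at information fraction t = 2/3, and an unadjusted final test.

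**Method.** Z1 is the interim statistic. With final information T relative to plan (T = 1 at 112), the final statistic is Z = [√t·Z1 + √(T−t)·Z2]/√T, with Z1 and Z2 independent standard normal under the null. Given Z1, the chance of rejecting is

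P(Z2 > [1.96√T − √t·Z1]/√(T−t)) + P(Z2 < [−1.96√T − √t·Z1]/√(T−t)),

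which is integrated over Z1. With T = 1 throughout, it returns 5.0%, as it should.

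**Uses the text describes**

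| Use | Total type I error |
|---|---|
| N from variability only (simulated, 37 then 56 per arm as planned, cap 2×) | 5.0–5.2% |
| Stop only if the effect points the wrong way | 2.5% |
| Stop unless the effect favours liraglutide at p < 0.5 / 0.2 / 0.1 | 2.4% / 2.1% / 1.6% |

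The stop-only rows assume that the stop is always obeyed. They fall below 5% because a directional stop removes nearly all claims against liraglutide.

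**Uses the text does not plan but does not exclude**

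| Use | Total type I error |
|---|---|
| Non-significant interims extended to T = 1.25 / 1.5 / 2 | 5.5% / 5.8% / 6.1% |
| N reset for 80% power at the observed effect: 74·(2.80/Z1)², held between 74 and 112 / 168 / 224 | 5.4% / 6.0% / 6.4% |
| Significance claimed at either of two looks at 1.96 | 7.7% (7.3% at t = 0.75, 7.1% at t = 0.80) |
| Worst case: N chosen after seeing Z1 to maximise rejection, cap 1.5× / 2× / 3× | 8.9% / 9.4% / 10.0% |

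**Power cost of the no-trend stop.** Assume 80% power without it (drift 1.96 + 0.84 = 2.80). Stopping when the effect is in the wrong direction leaves 80.0%. Stopping unless the effect favours liraglutide at p < 0.5, 0.2 or 0.1 leaves 79.5%, 75.6% or 69.2%. The plan does not say where in this range its criterion lies.

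**Which endpoint decides.** In Quantitative Traits, item 1 names gastric half-emptying time as primary and item 6 names peak postprandial hormone level, each within its own test. The aims also name weight loss. The interim section does not choose among them.

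**Blinding.** The allocation section describes blinding up to data lock. Item (b) sends between-arm summaries out earlier. Individual codes stay masked in both places. What is unreconciled is knowledge of comparative results.

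**The case against.** The strongest reply is that the plan describes only benign actions. Item (c) follows from the power analysis, item (a) bases that analysis on the observed COV, and the only named stop is for futility. On that reading error is about 5% or less, and the larger figures come from rules nobody wrote. This stands as far as it goes: the documents do not show inflated error. It does not settle the matter. No formula or target difference ties the power analysis to variability, and the team will have the effect in hand. Cutting N after a significant difference has been seen would work like an efficacy stop.

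On blinding, group medians do not reveal allocations, and an interim lock could be argued. A reader might infer that the blind is broken or that the investigator-blinding statement under Medication dispensing and delivery is contradicted. The documents do not support that.

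On bias, investigators already expect a benefit from earlier trials and their own pilot, several measures are instrumental, and counselling follows a set outline. That limits the risk, whose size is not shown. Buffet intake and satiation remain behavioural.

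A reader might also infer that sizing on the COV would sharply cut N if the drug works. With Table 5 values (mean 121.7, SD 29.8, healthy controls) and N scaled on COV², a 20 or 40 min slowing gives (121.7/141.7)² = 74% or (121.7/161.7)² = 57% of plan, but only from the active arm's COV. Within-arm SD over the overall mean gives (121.7/131.7)² = 85% or (121.7/141.7)² = 74%. The blinded pooled COV, whose variance gains 20²/4 or 40²/4, gives 95% or 107%. The text refers to the COV of the study, so no sharp cut follows.

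**Conclusion.** The concern holds in this form: a between-arm look is planned, its results leave the statisticians before lock, and N or the study's continuation may then change with no rule that protects the error rate. Type I error control is not assured. A reader might infer that the plan inflates type I error, but the documents do not support that, since its literal reading keeps error at about 5% or less. The range left open runs from there to about 10% (caps up to 3×), with 7.7% for two unadjusted looks. All these figures rest on the assumed two-sided 0.05 and look at two thirds of the information. The early release of comparative results is an avoidable bias risk of unknown size. It should be corrected before the interim, because disclosure cannot be reversed. The unnamed primary endpoint and missing planning values matter here only because they leave the interim without a basis for its decision.

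**What to change.** 1. **Item (a).** At a stated number of completers, re-estimate N only from the blinded pooled SD of one named endpoint, with a written formula, target difference, power and cap.
2. **Item (b).** Release no between-arm results to investigators or in abstracts before data lock; pooled or baseline data only. Reconcile this item with the blinding statement in Overall Design, Randomization and Allocation.
3. **Item (c).** Either delete the comparative look and the no-trend stop, or keep the look within the statisticians. If kept, name one deciding endpoint and who decides, and set an O'Brien-Fleming-type spending boundary: about p < 0.012 at the interim and p < 0.046 at the end for t = 2/3 (0.019 and 0.044 for t = 0.75), recomputed for the actual timing. Add a numeric, non-binding futility limit, for example conditional power below 20% under the planned effect. Allow no change in N based on the observed effect.

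Changes 1 and 2 suffice on their own only if the comparative part of (c) is deleted.

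**Cost.** Amendment wording, and no comparative interim abstract. If the look is kept, an assumed 80% power becomes 79.5%, or about 79% with the example futility limit obeyed. The blinded SD absorbs part of any true difference. At 0.53 SD, which 56 per arm detects with 80% power, the variance rises by 0.53²/4 = 7%, so N goes from 112 to about 120.
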